Official Title: Duration of Brace Wear in Clubfoot Treatment – A Prospective Randomized Trial

NCT Number: NCT01551264

Document Date: December 30, 2011

Duration of Brace Wear in Clubfoot Treatment – A Prospective Randomized Trial

RESEARCH DESIGN AND METHODS

Aim 1

- a. Establish the time dependent risk for relapse with need for further therapy in isolated clubfoot for 2 year versus 4 year bracing.
- b. Determine whether covariates that include compliance with bracing, gender, age, severity, and family history are associated with relapse.

Rationale

Based on the hypothesis that prolonged bracing will reduce clubfoot recurrence, we propose a multi-center, randomized, controlled trial evaluating the effectiveness of a 2 year versus 4 year bracing protocol in preventing clubfoot recurrence. No studies have previously assessed the length of bracing necessary to prevent clubfoot recurrence; therefore, the results of this study will have great clinical utility. When designing this trial, we sought to balance rigor with feasibility, and to maximize internal validity without sacrificing external validity.

Sample Size Justification and Statistical Power

The primary goal of this project is to determine the rate at which clubfoot recurs during the first year post-treatment. Because this primary goal involves estimation, we discuss sample size issues from the perspective of confidence bounds. *Table 1 presents the statistical power to detect between-group differences for various recurrence rates with the target enrollment sample size of 62 patients per group. Assuming a 10% dropout rate, with a total enrollment of 124 patients (55/group completing the entire trial) and observed recurrence rates of 10% versus 45%, statistical power will be excellent (0.99) to detect this between-group difference in recurrence rate of at least 35%.* That is, with 95% certainty, our estimate of the between-group difference in recurrence rate will be within 15% (50%-20%/2) of the true rate difference. Even with a more conservative estimate of the between-group difference, the study will have adequate power (0.80) to detect a between-group difference as small as 21%; where the recurrence rate in one group is 10% and the recurrence rate in the other group is as small as 31%.

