Two comments about the above computations are in order. First, we have estimated confidence bound widths using proportions instead of the Kaplan-Meier survival curves we will use in practice when we analyze the data. The reason is that we have no way at this time to estimate the standard errors that will result from the survival curves. During the early portions of the curve when we have complete data, we anticipate that the confidence bounds generated by the survival curves will be narrower than those presented above. By contrast, it is possible that the confidence bounds we generate for later portions of the curve may be wider than those presented above given the presumed number of dropouts. Second, we believe that independent of the standard errors resulting from the survival curves, our computed confidence bound widths are inherently conservative (i.e. we may get

narrower bounds in practice). The reason is that we anticipate in practice that the true dropout rate, particularly at earlier time points, will be less than the 10% that has been used in computing the number of subjects who provide data. Study dropouts will increase the study power because they will provide useful data up to the point of dropout. Thus, we believe that the presented power computations based on the sample of patients that complete the trial are conservative.

In addition to the reasons already presented, the provided power computations ensure a conservative estimate of sample size because they (1) utilize reoccurrence rates through 12 months of follow-up data only, and more patients will reoccur over time, and (2) have been performed using a dichotomous outcome measure whereas the data will be analyzed using survival analysis where follow-up on many patients will exceed 12 months. The primary analysis will enhance power by applying survival models and using a log rank test to compare time to reoccurrence between treatment groups.

Table 1. Recurrence rate between-group differences detectable with alternative incidences and a target enrollment of 124 patients (62 per group). Estimates based on two-tailed tests at alpha=0.05 comparing the rate of the event in two groups.

# of Patients in each Group		Detectable Relapse Rate at Specified Sample Size and Power			Power
Enrolled	With Complete Data*	Group 1	Group 2	Between-Group Difference (95% CI)	
62	55	10%	45%	35% (20%, 50%)	0.99
			40%	30% (15%, 45%)	0.96
			31%	21% (6%, 36%)	0.80

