Additional analyses include mixed model repeated measures analysis of variance to determine if the magnitude of changes in exam findings differs according to whether a recurrence ultimately occurs. Unlike traditional repeated measures analyses, the mixed model method allows for the inclusion of patients with incomplete data. The focus of these analyses will be the interaction between recurrence group and time point; interactions that test hypotheses regarding the equality of changes over time in the two groups. Within the mixed model, appropriate statistical contrasts will be used to test the null hypothesis that changes between two specific time points in one group are equal to corresponding changes in another group.

Simple t-tests and chi-square tests will be used to determine if characteristics at study enrollment differ according to whether there is recurrence. Receiver operating characteristic (ROC) curve analysis will be performed to determine if measures of compliance discriminate patients that recurrence from patients that do not recurrence.

These data will be analyzed with an "intention to treat" principle; wherein patients will be included in the intervention group as determined by the randomization, independent of compliance. Secondary analyses will be performed to evaluate the effects of treatment independent of crossover by examining outcomes relative to actual treatment status.

For all analyses, careful attention will be given to whether the data satisfy the distributional and model-specific assumptions of the procedures used. Appropriate data transformations or non-parametric methods will be used as appropriate.

It is important to point out that this study is not designed to (1) assess the safety or efficacy of a particular brace; (2) compare outcomes across clinical sites. All sites will use foot abduction braces. To avoid any perception of conflict of interest and to follow recommendations from the Disclosure Review Committee, the type of particular brace used will not be recorded in the study data. Brace type is inherently associated with clinical site and site physician. As such, the following variables will not be included as effects of interest in the analytic models: brace type, clinical site, physician, and orthotist.

Heat sensor data (analysis)

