While previous studies by our group and others have demonstrated that brace noncompliance is the number one risk factor for recurrence (Dobbs et al. 2004), these conclusions were made without objective measures of brace compliance. In prior studies, brace dose has been addressed simply as "compliance" or as an average number of hours worn.

Because we will use a heat sensor to objectively and accurately monitor compliance, compliance may be evaluated as both a continuous and a dichotomized measure. First, we will calculate the area under the curve to create one summary measure per patient per study period (or across the entire intervention period) as a continuous variable (i.e. average hours worn). For each individual, an area under the hours worn curve will be computed and the areas compared across between groups of patients who recurrence and those who do not. Second, we will analyze compliance as a dichotomized variable. For example, an adherer is someone who wears the brace for at least 80% of the prescribed time. The percentage of each group (recurrent patients versus non-recurrent group) who adhere to bracing regimen during each study time period (or across the entire intervention period) will be compared. Simple t-tests will be used to compare each group.

7. Data Management and Quality Control Activities

The first three months of this study will be spent establishing the infrastructure necessary to assemble data. **[The coordinator will need time to train personnel at participating site].** Prior to study start, the Coordinating Center (CC) will develop a data quality assurance plan and develop quality control procedures (QC) in accordance with the plan. The CC Research Coordinator will develop a Manual of Procedures (MOP) to address enrollment, patient safety monitoring, adherence to study procedures and timelines, and to facilitate consistency in protocol implementation and data collection across clinical sites. The MOP will specify the methods by which data is to be collected and related quality assurance procedures. The CC Coordinator will also provide dynamic training and certification of personnel across sites to ensure standardization of procedures.

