An "as-treated" analysis will be performed in addition to the primary intention-to-treat analysis to take into account the effect of crossover and dropout. It should be remembered that crossover occurs in the typical clinical setting whenever the patient either doesn't wear the brace at all, wears the brace at a less-than-effective dose, or when the patient or physician requests a brace after a period of observation. If a subject crosses over from observation to bracing treatment, we will be able to account for the patient's characteristics at the time of cross-over, and the dose monitor will allow measurement of subsequent time in brace. A 10 percent lost-to-follow-up rate has been taken into account in the sample size/power calculations. Although unrealistic, only a 0% rate of loss to follow-up guarantees the benefits of randomization. We will employ several proven strategies to minimize loss to follow-up, including education concerning the full burden of trial participation, minimization of respondent burden in terms of visits and questionnaires, obtaining at least one alternative contact for each subject, as well as phone calls and other reminders of upcoming visits. The seven centers have a documented ability to cover a 15% rate of dropout that is 5% greater than the estimate used for planning purposes. If dropouts exceed this during the recruitment phase, then centers from the alternate list will be brought into the study. If excessive dropouts occur during the follow-up phase of the study, no additional centers will be recruited and instead, attempts to locate the patient and determine final outcome will be made, and if needed, statistical methods will be employed to compensate for missing data.

Summary of Research Proposal

Clubfoot is a common and severe musculoskeletal birth defect. Although clubfoot is often successfully treated with the Ponseti method, some clubfeet relapse in the following years. One goal of this study is to provide clinically useful information regarding the optimal length of abduction bracing that is necessary to prevent clubfoot recurrence. A second goal of this study is to investigate the other variables (clinical, bracing compliance) that influence clubfoot recurrences. These studies have great potential to impact the care and treatment of patients with clubfoot.

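### The secondary as-treated analysis does not remove the effect of crossover or dropout: regrouping by treatment received breaks randomization, and the bias can run in either direction

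*Combined protocol and SAP*

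**What the plan says.** The primary analysis is by intention to treat. Under section 6, Statistical Analysis, General, the plan then states: "Secondary analyses will be performed to evaluate the effects of treatment independent of crossover by examining outcomes relative to actual treatment status". In the contingency section on crossovers, dropouts and loss to follow-up (its item 2) the as-treated analysis is added "to take into account the effect of crossover and dropout".

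Four other statements bear on this:

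- The crossover section lets families change treatment on request. It describes crossover as including a child who does not wear the brace or wears it too little.
- The heat sensor part of section 6 says that earlier studies showed "brace noncompliance is the number one risk factor for recurrence", while noting that those studies had no objective measure of wear.
- The crossover section says a child's characteristics at crossover can be accounted for. It names no method, and the sentence concerns a move from observation to bracing, although this trial has no observation arm.
- Elsewhere, Cox models take one covariate at a time, and propensity scores are reserved for a possible non-randomized cohort (contingency section, item 1, Patient Enrollment).

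**The concern.** Grouping children by the treatment they received gives an effect free of crossover only if switching is unrelated to prognosis. The plan's own statements point the other way: the behaviour that moves a child between groups is the one it names as the main predictor of the outcome. No named method in the plan repairs this.

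Regrouping does not correct informative loss to follow-up either. A child who leaves for reasons linked to relapse is lost from whichever group the child is placed in.

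What is at stake is interpretation. Power is 0.80 only for a 21-point difference, and crossover would dilute the intention-to-treat contrast. A non-significant primary result beside a significant as-treated result is therefore realistic. The present wording invites a reader to take the second as the effect with crossover removed.

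**Working it through.** **The plan's own figures.** The inputs are two-sided alpha 0.05 ("Estimates based on two-tailed tests at alpha=0.05 comparing the rate of the event in two groups"), power calculated "with the target enrollment sample size of 62 patients per group", and 55 per group with complete data. Power = Φ((d − 1.96·s0)/s1), where s0 is the pooled and s1 the unpooled standard error. For 10% v 31%: s0 = √(2·0.205·0.795/55) = 0.0770 and s1 = √((0.09 + 0.2139)/55) = 0.0743. Then (0.21 − 0.1509)/0.0743 = 0.795, so power is 0.787 (0.807 with the unpooled test; 0.80 stated). The other rows of Table 1 give 0.990 and 0.963 (0.99 and 0.96 stated). The planning figures reproduce and are not in question.

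**Assumptions for the as-treated comparison.** None of these is in the documents: true effect zero; overall risk 20%; a share q = 35% of poor adherers with risk ratio 2 or 3; a fraction c of the 4-year arm stopping at 2 years; a share f of those who stop being poor adherers; 62 per arm; no covariate adjustment.

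Good-adherer risk is g = 0.20/(0.65 + 0.35·RR) and poor-adherer risk is b = RR·g.
- RR 3: g = 0.1176, b = 0.3529.
- RR 2: g = 0.1481, b = 0.2963.

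Moving those who stop into the 2-year group gives

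false benefit = 2c(f − q)(b − g)/(1 − c²).

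For RR 3, c = 0.20, f = 1: 2·0.20·0.65·0.2353/0.96 = 0.064. Group sizes are 62·1.2 = 74.4 and 62·0.8 = 49.6, with s0 = 0.0733 and s1 = 0.0713. Rejection favouring 4 years is Φ((0.0637 − 1.96·0.0733)/0.0713) = 0.131. The other tail adds 0.002, for a total of 13%.

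| RR | c | f | As-treated risk, 2-year v 4-year | False benefit (points) | Two-sided error |
|---|---|---|---|---|---|
| 3 | 20% | 100% | 22.5% v 16.2% | 6.4 | 13% |
| 3 | 20% | 70% | 21.4% v 17.9% | 3.4 | 7% |
| 3 | 20% | 50% | 20.6% v 19.1% | 1.5 | 5% |
| 3 | 10% | 100% | 21.4% v 18.3% | 3.1 | 7% |
| 2 | 20% | 100% | 21.6% v 17.6% | 4.0 | 8% |
| 2 | 10% | 100% | 20.9% v 18.9% | 2.0 | 6% |

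These rows vary one or two inputs at a time. Milder combinations fall below the table: RR 3 with c = 10% and f = 50% gives 2·0.10·0.15·0.2353/0.99 = 0.7 points. At f = q the bias is zero.

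**Switching in both arms.** Take the first row and let 10% of the 2-year arm (6.2 children, all good adherers) continue.
- 2-year group: (12.4 − 6.2·0.1176 + 12.4·0.3529)/68.2 = 16.05/68.2 = 23.5%.
- 4-year group: (12.4 − 12.4·0.3529 + 6.2·0.1176)/55.8 = 8.75/55.8 = 15.7%.
- The false benefit is 7.8 points with 19% error. With RR 2 it is 4.9 points and 10%.

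Intention-to-treat compares 20% with 20% throughout.

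**A second set of assumptions, simulated with 55 per arm.** Here 30% of children have poor prognosis (risk 45% v 10% in the rest), and 50% of them and 5% of the others stop early in the 4-year arm.
- Switchers: 0.3·0.5 + 0.7·0.05 = 18.5%. They carry 0.15·0.45 + 0.035·0.10 = 0.071 of the arm's events.
- As-treated risks: (0.205 + 0.071)/1.185 = 23.3% v (0.205 − 0.071)/0.815 = 16.4%, a difference of 6.8 points.
- Simulated error: 13.1%, against 4.9% for intention-to-treat.
- Same switching placed in the 2-year arm (poor-prognosis children extending): −6.8 points and 13.1%.
- Equal prognosis-related switching in both directions: zero bias.
- Switching unrelated to prognosis (30% of the 4-year arm): zero bias, error 4.8%.

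**The case against.** The strongest reply has four parts.

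*The analysis is secondary.* Intention-to-treat is primary, and nothing in the plan ranks as-treated above it. This stands and limits the point to interpretation.

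*The plan will account for characteristics at crossover, and wear is measured objectively.* This is a partial answer. No method is named, and the sentence describes a switch that cannot occur in this trial. Measuring wear well does not make those who wear the brace comparable with those who do not.

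*The larger figures depend on near worst-case inputs.* This is fair. The 13% figure needs every child who stops to be a poor adherer, and the 19% figure also needs every child who continues to be a good one. At 50-70% poor adherers the error is 5-7%. A reader might infer that as-treated will favour 4 years. The documents do not support a fixed direction: higher-risk children in the 2-year arm extending bracing would favour 2 years, and equal prognosis-related switching in both directions would cancel.

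*Dropouts do contribute.* A reader might infer that they have no outcome at all. The documents say otherwise. The sample size section counts their data up to dropout. The crossover section keeps participants in follow-up unless consent is withdrawn and foresees missing-data methods if needed. What remains is that regrouping by treatment received does not itself correct informative loss.

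The complier-average remedy has difficulties of its own. Section 5 (Study Endpoint) sets assessment one year after each arm's bracing ends, so assignment changes the time of assessment. Section 3 (Casting and Bracing Protocol) returns a child to the brace after recurrence, so the outcome can alter the bracing received. Both must be handled in the definition.

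**Conclusion.** The concern holds as a claim about what the as-treated analysis can deliver. It does not give an effect free of crossover and does not account for dropout. It can be biased toward either arm, depending on who switches.

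With one-directional early stopping in the 4-year arm and no true effect, the tabulated scenarios give about 1.5 to 6 points and 5-13% two-sided error, rising to 8 points and 19% with opposite selection in the 2-year arm. These sizes rest wholly on assumed crossover rates, subgroup share and risk ratios; weaker assumptions give less and stronger ones more. That switchers differ in prognosis is implied by the plan's statements but cannot be measured from the documents.

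A reader might go further and infer that the trial's main conclusion is compromised. That is not supported: the primary intention-to-treat analysis, its alpha and the sample size are untouched.

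**What to change.** 1. Delete the claim in the General analysis section that the effect is evaluated free of crossover, and the claim in the crossover section that as-treated accounts for dropout.
2. Label the as-treated analysis descriptive, and state that conclusions rest on intention-to-treat.
3. Prespecify a complier-average estimate as a sensitivity analysis: the intention-to-treat risk difference divided by the between-arm difference in the proportion braced beyond 2 years, with a bootstrap interval.
4. When defining braced beyond 2 years, count only bracing before any recurrence, so that the outcome does not determine the classification.
5. For this estimate, compare risk at a common time from the start of bracing, fixed in advance and reached by follow-up in both arms, so that assignment does not act through a different assessment time.

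**Cost.** Plan wording and one extra analysis on data the trial already intends to collect, provided the 2-year arm is followed to the common time. The interval widens. If 20% of the 4-year arm stops and nobody in the 2-year arm continues, the divisor is 0.80 and the interval is about 1/0.80 = 1.25 times as wide. With 10% also continuing it is 1/0.70 = 1.43 times. Counting only bracing before recurrence lowers the divisor further. The estimate also assumes that assignment acts only through bracing beyond 2 years, which the data cannot verify.

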Study subjects will be seen every 3 months. Interim visits for brace fitting and consultation or family discussions with the physician/coordinator/orthotist will be allowed and encouraged. Local coordinators will contact the patient and family via phone at least monthly to provide the opportunity for questions, discussion, and feedback as needed. Subjects will be evaluated at each visit of the current state of their clubfoot and will be told if there are any signs of recurrence. Parents have the right to withdraw from the study at anytime.

5. Study Endpoint

Although follow-up data will be collected for the duration of the trial, the data collected at 1-year follow-up post completion of treatment arms will be used for the primary analysis to address the question asked in specific aim 1a. This ensures that patients in both treatment arms are followed for the same amount of time after they finish bracing.

6. Statistical Analysis

General

The goal of this study is to establish the time-dependent risk for recurrence within the first year post-treatment and evaluate factors associated with recurrence in isolated clubfoot. Kaplan-Meier survival curves that describe the time to recurrence will be generated, with

95% confidence bounds placed around the probabilities that this event will occur at pre-defined intervals. Of particular interest will be an assessment of the hazard ratio, with 95% confidence bounds, that compares recurrence in patients receiving 2-year versus 4-year bracing. While the goal of this study is to detect an overall treatment difference, Cox regression analysis will determine whether covariates that include compliance with bracing, gender, laterality, age, Pirani score, and family history are associated with the probability that relapse will occur. A separate Cox model will be used for each covariate.

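### Aim 1b compares hours worn by recurrence without stopping the record at relapse; whole-period hours also need scaling to prescription and an account of arm

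*Combined protocol and SAP*

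**What the plan says.** Aim 1b is to "Determine whether covariates that include compliance with bracing, gender, age, severity, and family history are associated with relapse". Three parts of section 6 (Statistical Analysis) serve it.

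- **Heat sensor data.** Each child gets "one summary measure per patient per study period (or across the entire intervention period) as a continuous variable (i.e. average hours worn"). Then "For each individual, an area under the hours worn curve will be computed and the areas compared across between groups", recurrent against non-recurrent, by t-test. A dichotomised version is given as an example: "an adherer is someone who wears the brace for at least 80% of the prescribed time".
- **General, Cox regression.** "Cox regression analysis will determine whether covariates that include compliance with bracing, gender, laterality, age, Pirani score, and family history are associated" with relapse, and "A separate Cox model will be used for each covariate". The text does not define the compliance covariate and does not mention arm or time-dependent coding.
- **General, ROC analysis.** This is planned "to determine if measures of compliance discriminate patients that recurrence from patients that do not recurrence".

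Section 3 (Casting and Bracing Protocol) sets wear at 23 hours a day for three months and then eight to twelve hours at night, for 2 or 4 years by arm. Every brace carries a logger. Recurrence is treated by casting again and then bracing again, and its definition has no time window. The General part of section 6 gives the study goal as the "time-dependent risk for recurrence within the first year post-treatment and evaluate factors associated with recurrence in isolated clubfoot". Section 5 (Study Endpoint) ties the explicit one-year rule to Aim 1a only.

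**The concern.** Three things other than the family's compliance can move the hours recorded.

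1. **Relapse itself.** It interrupts wear during casting and restarts it afterwards. If that part of the record stays in, the outcome alters the exposure that is meant to predict it.
2. **Phase.** Prescribed wear falls sharply after three months, so an average depends on how long the record runs.
3. **Arm.** Total prescribed hours differ by design. If recurrence differs by arm, as the trial hypothesises, total hours will differ by recurrence even when every child complies equally.

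The first applies to any summary that includes time after a relapse. The second and third matter for whole-period or total summaries, much less for averages over periods common to both arms. A Cox model with one fixed value per child has the same weakness, because the value includes wear that occurs after the times at risk.

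The sensors were introduced because earlier compliance findings lacked an objective measure. An association produced by the bookkeeping would defeat that purpose. Its sign is also open, since total and average hours can be biased in opposite directions.

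**Working it through.** **1. The plan's own figures.** No power or error figure is given for the compliance analysis. Table 1 supplies the recurrence rates used below. With 55 per arm and two-sided 0.05, power = Φ{[d√n − 1.96√(2p̄(1−p̄))] / √(p₁(1−p₁)+p₂(1−p₂))}. This gives 0.990, 0.963 and 0.787 for 10% against 45%, 40% and 31%; Table 1 states 0.99, 0.96 and 0.80.

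**2. Prescribed hours (section 3 read literally: three months at 23 h, then 24 or 48 months of nights; 30.44 days a month; 10 h a night assumed within the stated 8–12).**
- 2-year arm: (23×3 + 10×24)×30.44 = 309×30.44 = 9,406 h. Average 309/27 = 11.4 h/day.
- 4-year arm: (23×3 + 10×48)×30.44 = 549×30.44 = 16,712 h. Average 549/51 = 10.8 h/day.
- Ratio of totals: 549/309 = 1.78. At 8 h, 453/261 = 1.74; at 12 h, 645/357 = 1.81. If the three months count inside the 2 or 4 years, 519/279 = 1.86.

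**3. Arm alone, everyone fully compliant, 45% (taken as the 2-year arm) v 10%.**
- Total, recurrent: (0.45×9,406 + 0.10×16,712)/0.55 = 10,734 h. Non-recurrent: (0.55×9,406 + 0.90×16,712)/1.45 = 13,940 h. Recurrent children look about 3,200 h worse.
- Average, same weights: 11.32 v 11.02 h/day. Recurrent children look slightly better.

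**4. A cut-off alone.** A fully compliant child who relapses at month 12 has 23×3 + 10×9 = 159, that is 159×30.44 = 4,840 h in total and 159/12 = 13.25 h/day. The total is far below the full-period figures and the average is 1.8 to 2.5 h/day above them. Worn over prescribed is 159/159 = 100%, as for every other fully compliant child.

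**5. False-positive rates with no compliance effect (nominal 5%).** Assumed: 55 per arm; 10 h a night; steady adherence with mean 0.75 and SD 0.15; follow-up to 12 months after bracing; relapse at 5–10% a year from brace start, or only after bracing at the rates shown. Wear was set to none for six weeks after relapse and then resumed, for the calculation only. Periods of 0–3, 3–12 and 12–24 months are assumed, because the plan defines none. At least 1,000 trials per case; t-test.

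| Summary of wear | Recurrences | Rejections |
|---|---|---|
| Whole-period average, uncut | from brace start | about 10–19% |
| Per-period average, uncut | from brace start | about 10–25% |
| Per-period average, cut at relapse | from brace start | about 5–6% |
| Whole-period average, cut, unscaled | from brace start | 78–93% |
| Total hours, cut, unscaled | from brace start | 95–99% |
| Worn/prescribed, cut | from brace start | about 5% |
| Total hours | after bracing, 45% or 31% v 10% | 95% or 62% |
| Whole-period average | after bracing, 45% or 31% v 10% | 11% or 6% |
| Total or average | after bracing, equal rates | about 5% |

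**6. Sensitivity to assumptions.** A second set used Beta(6,2) adherence, 25% recurrence in both arms and relapses from month 6. With 0, 2 or 4 months in cast, the uncut whole-period average rejects in 5%, 15% or 34%. The uncut 80% measure rejects in about 5%, 14% or 36%, and a Cox model on one fixed average per child, without arm, in 4%, 12% or 31%. At 45% v 10% with two months in cast, the arm and casting effects on the average nearly cancel (5%). Worn/prescribed, cut at relapse and adjusted for arm, gave 4–6% in every case of this set.

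**7. The 80% rule.** Eight hours of wear is 8/8 = 100% or 8/12 = 67% of prescription, on either side of the threshold.

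**The case against.** The strongest reply is that the alarming rates belong to readings the plan does not clearly state. It glosses the area as average hours, names per-period summaries first, and nowhere says that the record stops at relapse. For period averages under steady wear, a cut-off alone suffices. All of that stands, and it limits the scaling and arm gaps to whole-period or total summaries.

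Second, if Aim 1b follows the stated goal of first-year post-treatment recurrence, wear during the intervention precedes every counted event. The cut-off is then moot and the average-hours distortion is small (about 6–11%). That stands too, but the plan does not settle the window for Aim 1b.

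Third, a constant yearly rate with longer follow-up in the 4-year arm gives more recurrence there: 1−0.95^3.25 = 15% v 1−0.95^5.25 = 24%, or 29% v 42% at 10% a year. This runs against the trial's hypothesis, so the rates from brace start are illustrations and not forecasts.

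A reader might infer that arm is excluded from the compliance Cox model. One model per covariate does not say so; the text is only silent. A reader might also infer that the main result is at risk. The primary comparison is a log-rank test by randomised arm and uses no sensor data.

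None of these replies supplies a cut-off, a denominator or a covariate definition. The general promise to check model assumptions does not either.

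**Conclusion.** The point holds for secondary Aim 1b and should be fixed before analysis. The omissions and the 1.78-fold difference in prescribed hours follow from the text, the ratio varying only between 1.74 and 1.86 with night hours and how the three months are counted. The error rates rest on assumed adherence, relapse timing and time in cast.

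On the plainest readings the distortion is modest: about 10–19% for an uncut whole-period average (5–34% across the second set of assumptions) and about 10–25% for uncut per-period averages. It becomes large only if total hours are used while recurrence differs by arm (62–95%), or if unscaled whole-period hours are merely cut at relapse (78–99%). It would be wrong to conclude that the planned analysis is bound to fail at those higher rates, or that adding a cut-off alone would repair it. The 80% measure is already scaled to prescription, but it has neither a cut-off nor a single denominator.

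**What to change.** In section 6 (General and Heat sensor data):

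1. Replace the raw area with hours worn divided by hours prescribed, counted only up to first recurrence. The cut-off and the scaling must be introduced together.
2. State one night-time denominator for analysis. This is an analysis definition and leaves the wear instruction as it is.
3. Make the already planned Cox model the main compliance analysis, stratified by arm. Enter the cumulative proportion as a time-dependent covariate, held at its last value once bracing ends.
4. Use the same proportion, cut at relapse and over a window common to both arms, for the 80% comparison and the ROC, accounting for arm.
5. State whether Aim 1b counts recurrences from brace start or only in the first year after bracing.

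A lag of one 3-month download interval and a 12-month landmark are reasonable sensitivity analyses. They guard against wear that wanes over time or falls just before diagnosis; both patterns are assumptions and are not in the documents.

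The cost is SAP wording and some programming. Sensor data are already downloaded every three months, so no new collection is needed. Under the step 5 assumptions, the lag would drop about 1–3 of 21–22 recurrences at 5% a year, or 3–5 of 39 at 10%. The landmark would drop about 5–6 of 21–22, or 11 of 39.
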